1.0 BACKGROUND AND RATIONALE

1.1 Study Disease

Due in part to the widespread use of abdominal imaging procedures, the incidence of renal tumors has incremented exponentially over the last several decades [1]. The National Cancer Institute estimates the incidence of new cases of renal cell carcinoma in 2011 at 60,920 [2]. The increasing detection of incidental small renal masses on abdominal imaging has been accompanied by a clear downward stage migration, such that by 2007, close to 60% of renal tumors measured < 4 cm [3, 4]. Indeed, about 50% of the patients referred to urologists today for suspected renal malignancy have incidentally discovered asymptomatic small renal masses [5].

Importantly, the highest incidence of these tumors is seen in elderly patients, who usually present with a number of comorbidities[6]. In treating patients with renal masses, three competing factors have to be balanced: cancer control, patient morbidity, and preservation of renal function.

Preservation of renal function is a key factor in survival. With mounting evidence highlighting the importance of renal preservation [7-10] and documentation of the oncologic efficacy of partial nephrectomy [11], the American Urological Association's guidelines currently place partial nephrectomy as the standard of care for the management of T1a tumors (< 4 cm) and as an alternative treatment option for T1b tumors (4-7 cm) [12]. Reflecting this paradigm shift, the use of partial nephrectomy has risen substantially at many centers of excellence over the past decade, approaching 90% for T1a tumors [13].

With evidence demonstrating improved patient survival following partial rather than radical nephrectomy, nephron-sparing surgery (NSS) has become the standard of care for the management of T1a renal tumors and an accepted alternative for the management of T1b tumors [14, 15]. Furthermore, as the use of minimally invasive technology has advanced within the urologic community, laparoscopic partial nephrectomy and robot-assisted partial nephrectomy (RAPN) have been established as viable alternatives to open NSS [16, 17].

Open NSS traditionally involves clamping of the renal hilar vessels and an abundant use of ice to ensure tissue hypothermia. However, techniques of achieving kidney hypothermia have not been translated to minimally invasive NSS. Thus, renal hilar clamping during minimally invasive NSS is performed under warm ischemia. Increased duration of warm ischemia time (WIT) has been demonstrated to negatively impact short and long-term renal function [18]. As a result, many techniques for limiting WIT have been described, including segmental renal artery clamping, renal parenchymal clamping, early unclamping, and unclamped NSS following administration of hypotensive agents [19-22].

Several years ago, the Principal Investigator developed a technique where RAPN is performed without clamping of the renal hilar vessels and without systemic blood pressure manipulation. This technique is applicable to all renal tumors that are appropriate for partial nephrectomy.

In order to determine the efficacy of this procedure, a retrospective chart review, matched cohort study was performed at Washington University comparing 29 patients who underwent off-clamp RAPN for suspected renal cell carcinoma with a matched 29 patients that underwent RAPN with hilar clamping. The procedures were performed from 3/2008 to 9/2011, and the patients in each group were similar in nephrometry score and baseline renal function. The off-clamp patients experienced an estimated blood loss of 146.4cc, while the hilar clamped RAPN group had an estimated blood loss of 103.9cc ($p=0.039$). The complications were similar in the two groups with no complications seen in the off-clamp group and only one Clavien-2 complication in the hilar clamp group. The mean eGFR decline was 4.9 ml/min/1.73m² in the off-clamp group and 11.7ml/min/1.73m² in the hilar clamp group ($p=0.033$). In summary, the off-clamp RAPN patients experienced less decline in renal function while experiencing similar morbidity [23].

These preliminary results have shown comparable perioperative outcomes to traditional clamped RAPN, while mitigating renal functional damage and providing excellent oncologic control. To date, we have submitted for publication: 1) video and detailed description of our off-clamp RAPN technique, 2) safety and efficacy of this technique in our initial 42 patient experience, 3) safety and efficacy of our technique for technically difficult renal tumors, and 4) a retrospective matched cohort study comparing off-clamp to clamped RAPN. We aim to prospectively compare renal functional, perioperative and oncologic outcomes between our off-clamp technique and traditional clamped RAPN.

1.2 Rationale

Randomizing patients to either traditional clamped RAPN or off-clamp technique will allow for prospective data in regards to the effect of hilar clamping on renal function. We hypothesize that the off-clamp RAPN technique will lead to decreased decline in renal function compared to the on-clamp RAPN.

2.0 OBJECTIVES

2.1 Primary Objective

1. To determine if off-clamp RAPN technique better preserves long-term renal function than the traditional clamped RAPN technique.

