5.4 Postoperative Care

The postoperative management is standard of care for all patients who undergo RAPN.

Three month post op visit:

- CR/eGFR
- Renal Scan
- CT/MRI of abdomen
- Chest x-ray (CXR)

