5.5 Duration of Follow-Up

The follow up management is standard of care but uniquely different for patients based on pathologic outcome. Patients with a malignant (cancerous) surgical pathology will be followed for a period of 3 years. Patients with a benign (non-cancerous) surgical pathology will only be followed through a period of 3 months postoperatively. Patients removed from

this study for unacceptable adverse events will be followed until resolution or stabilization of the adverse event.

Yearly follow up visits:

- CR/eGFR
- CT/MRI of abdomen
- Chest x-ray (CXR)

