9.0 STATISTICAL CONSIDERATIONS

9.1 Study Objectives and Endpoints

Primary Outcome:

Evaluation of renal function following RAPN with or without hilar clamping using:

1. Decline in estimated glomerular filtration rate (eGFR). eGFR is calculated from serum creatinine using the Chronic Kidney Disease Epidemiology Collaboration formula [11]. Decline in eGFR = Postoperative eGFR – Preoperative eGFR.
2. Decline in split renal function (SRF). SRF is a percentage of the total renal function supplied by one kidney. Ideally each kidney has a SRF of 50%. SRF is measured during renal scintigraphy (renal scan). Decline is SRF =preoperative SRF- postoperative SRF (3 month).

Secondary Outcomes:

1. Oncological outcomes:
 - a. Pathological results
 1. Pathologic margin status
 2. Tumor histology, including Fuhrman grade if applicable
 3. Distance between tumor margin and surgical margin

- b. Evidence of disease recurrence or metastasis on follow-up imaging
 - 1. Recurrence free survival
- 2. Perioperative outcomes
 - a. Estimated blood loss
 - b. Operative time and warm ischemia time
 - c. Intra-operative complications, including but not limited to injury to the surrounding organs and vessels, excessive blood loss requiring blood transfusions, and conversion to radical nephrectomy or open surgery.
 - d. Length of postoperative hospital stay
 - e. Postoperative complications, including but not limited to urine leak, urinoma, abscess, pseudoaneurysm, ileus, blood transfusion requirements, incisional hernias, wound infection, blood transfusion requirements, deep venous thrombosis, pulmonary embolism, myocardial infarction, stroke, and death.

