APPENDIX C: Study Schedule of Events

	Pre-Operative Assessments	Surgery	Post-Operative Assessments		
	Baseline ¹	RAPN	1 day Post RAPN	3 months Post RAPN	Every 12 months ²
Informed Consent	X				
Demographics	X				
Medical & Surgical History	X				
Height & Weight	X				
Serum Creatinine/eGFR	X		X	X	X
Renal Scan	X ¹			X	
CT/MRI of abdomen	X ¹			X	X
CXR	X ¹			X	X
Incl./Excl. Criteria Confirmation	X				
Randomization		X			
Perioperative Outcomes		X			
Pathology results		X			
Adverse Event Assessment				X	
Assessment of Evidence of Disease Recurrence				X	X

¹ Scans (Renal Scan, CT/MRI of abdomen and Chest Xray (CXR)) performed prior to or at time of baseline assessments per standard of care

² From the date of 3-mo follow up for total of 3 years only for patients with malignant pathological outcome

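### The primary objective is long-term renal function, but the last renal-function measurement planned for every randomised patient is at 3 months, and the primary eGFR outcome names no visit

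*Combined protocol and SAP*

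**What the plan says.** The primary objective in section 2.1 is "To determine if off-clamp RAPN technique better preserves long-term renal function than the traditional clamped RAPN technique". No section puts a number of months or years on long-term. Section 1.1 treats short and long term as different things: "Increased duration of warm ischemia time (WIT) has been demonstrated to negatively impact short and long-term renal function". The hypothesis in section 1.2 has no time horizon: "We hypothesize that the off-clamp RAPN technique will lead to decreased decline in renal function compared to the on-clamp RAPN".

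Section 9.1 lists two primary outcomes. The first is "Decline in eGFR = Postoperative eGFR – Preoperative eGFR", with no visit attached. The second is decline in SRF, defined as the preoperative value minus the postoperative value and fixed at 3 months.

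On follow-up, section 5.4 lists creatinine/eGFR and the renal scan together under "Three month post op visit", without restriction by pathology. Section 5.5 then separates patients by histology: "Patients with a malignant (cancerous) surgical pathology will be followed for a period of 3 years", but "Patients with a benign (non-cancerous) surgical pathology will only be followed through a period of 3 months postoperatively". In Appendix C the renal scan row stops at 3 months. The eGFR row continues every 12 months, with a footnote: "From the date of 3-mo follow up for total of 3 years only for patients with malignant pathological outcome". Section 7.0 lists the follow-up data sheet at 3 months and yearly after that, and does not mention pathology.

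**The concern.** The objective is comparative and carries a time horizon, so a reader expects a renal-function measurement at that horizon in both arms and in all randomised patients. The schedule provides that only up to 3 months. Beyond it, one primary outcome is not measured at all and the other is measured in a subset identified only after surgery.

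Two things are at stake. A report that follows the plan would either set a 3-month result against a long-term objective, or answer the long-term question for eGFR alone and only in patients with malignant tumours. And because several eGFR readings fit the primary definition, nobody could verify afterwards that the reported value was the planned one. Opposite signs for the two declines add a practical risk of misreading the direction of effect.

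**Working it through.** The plan has no figure of its own to reproduce here: section 9.2 gives about 80 patients (40 per arm in section 5.2.1) without a power calculation. The check is a reading of the schedule.

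**Step 1: what is scheduled, and in whom.** Section 3.1 requires an organ-confined renal mass, not proven malignancy, so benign tumours can be randomised. Combining sections 5.4, 5.5, 9.1 and Appendix C:

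| Postoperative occasion | eGFR, malignant | eGFR, benign | SRF, malignant | SRF, benign |
|---|---|---|---|---|
| Day 1 | yes | yes | no | no |
| 3 months | yes | yes | yes | yes |
| Yearly | yes | no | no | no |

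The 3-month row is the last one filled for everybody. SRF after 3 months is scheduled for 0 of about 80 patients.

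**Step 2: how many eGFR readings fit the primary definition.** Every postoperative value satisfies the formula in section 9.1.

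- Benign: day 1 + 3 months = 2.
- Malignant, three years counted from the 3-month visit: yearly visits at 15, 27 and 39 months, so 2 + 3 = 5.
- Malignant, both the years and the visits counted from surgery: 12, 24 and 36 months, so 2 + 3 = 5.
- Malignant, visits spaced from the 3-month visit (Appendix C footnote) but follow-up ending three years (36 months) after surgery (one reading of section 5.5): 15 and 27 months only, because 39 > 36, so 2 + 2 = 4.

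The count is therefore 4 or 5 against 2.

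**Step 3: does any section choose among them?** Section 5.4 makes 3 months the natural choice, since eGFR and the renal scan fall at the same visit, but it does not say that this eGFR is the primary value. Section 9.3 lists what will be summarised and names neither eGFR nor SRF. The matched-cohort result in section 1.1 gives mean eGFR declines without saying when they were measured. None of these settles the visit.

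**Step 4: direction of the two formulas.** With eGFR as postoperative minus preoperative, a loss of size L gives −L. With SRF as preoperative minus postoperative, a loss of size L gives +L. Section 1.1 reports eGFR declines as positive numbers, 4.9 off-clamp and 11.7 clamped (ml/min/1.73m²); the formula in section 9.1 would give −4.9 and −11.7. Better preservation then shows as the larger value for eGFR and the smaller value for SRF.

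**Step 5: size of the subset.** If a share b of the 80 patients has benign pathology, at most 80 × (1 − b) have eGFR scheduled after 3 months. The documents do not give b, so no figure for lost patients or lost precision is offered, and the point does not need one.

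**The case against.** The strongest reply has four parts.

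*Longer-term eGFR is collected.* True: yearly over three years, in both arms. A reader might infer that the trial has no renal data beyond 3 months; the documents do not support that. What stands is that these data cover one of two primary outcomes in one pathology group, and that nothing ties them to the primary outcome. Section 7.0 could suggest that annual data are expected from everyone. Section 5.5 and the Appendix C footnote state the malignant-only limit explicitly, so they are followed here, but the three places need to be reconciled.

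*Three months may be what the protocol means by long-term, as against day 1.* This cannot be excluded, because the term is undefined. The supportable statement is therefore that nothing is measured after 3 months for SRF, not that long-term SRF is absent by definition. If 3 months was meant, the objective should say so.

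*Ending benign follow-up at 3 months is standard of care.* Section 5.5 says that follow-up management is, and it is a reasonable feasibility choice. The fault is that the objective reaches beyond it. A reader might also infer that a comparison within malignant patients is biased between arms. The documents do not support that: the rule is the same in both arms, and clamping cannot plausibly change histology. The cost is fewer patients and a narrower population.

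*The analysis is only descriptive.* A descriptive summary still needs a named visit, and the objective asks which technique preserves function better. Opposite signs are a matter of notation and would not invalidate data, but both lines are labelled as decline and only one behaves as one.

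**Conclusion.** Wrong as written. The primary objective does not match what is measured in all randomised patients. After 3 months, SRF is scheduled in nobody and eGFR only in malignant pathology; the primary eGFR outcome can be any of 4 or 5 readings in malignant and 2 in benign patients; and the eGFR decline formula turns a loss into a negative number.

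This rests on the text and schedule alone, with one reading choice: that the explicit limit in section 5.5 and Appendix C governs over the unrestricted entry in section 7.0. If section 7.0 governed, later eGFR might exist for everyone, but SRF would still stop at 3 months and the eGFR visit would still be unnamed. The point should be corrected. It does not show that the comparison between arms is biased or that the follow-up rule itself is unsound.

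**What to change.** - **Section 9.1:** define the primary eGFR outcome as preoperative eGFR minus 3-month eGFR in all randomised patients, malignant and benign, so that it shares its visit and sign with SRF.
- **Section 2.1:** replace long-term with 3-month, so that the primary conclusion is limited to what is measured in everyone. Section 1.2 needs no change.
- **Section 9.3:** state that both 3-month declines are reported by randomised arm, that day-1 eGFR is secondary, and that annual eGFR is a secondary analysis in malignant-pathology patients.
- **Sections 5.5, 7.0 and Appendix C:** reconcile who has annual follow-up and say when the three years start.

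This costs wording only, because section 5.4 already schedules both measurements at 3 months for all patients. The downside is a narrower primary claim, and the sponsor should accept it knowingly, since it changes the stated question.

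If the sponsor prefers to keep long-term, it would need to define the term and name a later eGFR visit for all randomised patients. That adds visits for those with benign pathology, so it is not the cheap option, and SRF would still end at 3 months.

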2.2 Secondary Objectives

1. To determine if oncologic outcomes are equivalent between off-clamp and traditional clamped RAPN.
2. To determine if the complication severity and rates are equivalent between off-clamp

technique and traditional clamped RAPN.

3. To determine if off-clamp RAPN technique requires longer operative times or prolongs hospital stay.
4. To determine if off-clamp RAPN technique causes greater blood loss during surgery.

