5.2 Operative Procedure

5.2.1. Randomization

Randomization will take place in the operating room, after feasibility of RAPN off clamp is confirmed. Patients will be randomized to either off-clamp RAPN or traditional clamped RAPN in a 1:1 ratio, for a total of 40 patients allocated to each group. To minimize selection bias, a randomization table will be developed before initiation of enrollment.

Envelopes containing randomization assignments will be created, sequentially numbered and sealed. Once enrollment is initiated, randomization envelopes will be opened for each subject after informed consent is granted and study eligibility is confirmed in the operating room.

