6.2 Measurement of Post-Operative Complications

In addition to reporting AEs according to the CTCAE (as described in Section 6.1), postoperative complications will be reported using the Clavien-Dindo Classification of Surgical Complications Appendix B. Adverse Events and Complications will be assessed from time of study intervention to the three month post visit.

The principal investigator will also determine complications based on normal standards.

Complication Examples:

1. Intra-operative complications for a RAPN include but are not limited to injury to the surrounding organs and vessels, excessive blood loss requiring blood transfusions, and conversion to radical nephrectomy or open surgery.
2. Postoperative complications for RAPN include but are not limited to urine leak, urinoma, abscess, pseudoaneurysm, ileus, blood transfusion requirements, incisional hernias, wound infection, blood transfusion requirements, deep venous thrombosis, pulmonary embolism, myocardial infarction, stroke, and death.

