9.3 Data Analysis

Data analysis for this study will be descriptive in nature. Demographic and clinical characteristics of the sample, as well as local recurrence and post-surgery complications will be summarized using descriptive statistics. Kaplan-Meier product limit method will be used to estimate the 2-year overall and disease-free survival. The median disease-free survival, overall survival and their 95% confidence interval will also be estimated.

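### Secondary objectives 1 and 2 promise to determine equivalence, but the analysis is descriptive, with no margin, no between-arm difference and no interval on one

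*Combined protocol and SAP*

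**What the plan says.** Section 2.2 lists four secondary objectives. The first is "To determine if oncologic outcomes are equivalent between off-clamp and traditional clamped RAPN". The second begins "To determine if the complication severity and rates are equivalent between off-clamp" and names traditional clamped surgery as the comparator.

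The outcomes that would inform these objectives are collected. Section 9.1 lists "Pathologic margin status", tumour-to-margin distance, recurrence and recurrence-free survival, along with intra-operative and postoperative complications. Section 6.2 says "postoperative complications will be reported using the Clavien-Dindo Classification of Surgical Complications", with assessment from the intervention to the three-month visit.

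The analysis is in section 9.3: "Data analysis for this study will be descriptive in nature". It adds that "local recurrence and post-surgery complications will be summarized using descriptive statistics" and that "Kaplan-Meier product limit method will be used to estimate the 2-year overall and disease-free survival". The only confidence interval mentioned is a 95% interval given with median disease-free and overall survival. The section speaks of the sample and does not say that results will be shown by arm.

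The sample size in section 5.2.1 is "for a total of 40 patients allocated to each group". No margin, significance level, power or sample-size rationale appears anywhere.

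**The concern.** To determine equivalence is to show that the true difference between arms lies inside a range judged unimportant beforehand. That needs a margin and an interval or test on the difference. Section 9.3 has neither, so the objective and the analysis promise different things.

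What is at stake is what the trial can say about the safety and cancer control of the off-clamp technique. If renal function favours off-clamp surgery, readers will next ask whether that comes at a price in complications, margins or recurrence. A table of similar-looking rates, set beside an objective worded as equivalence, would invite the answer that there is no price. With 40 per arm the data cannot carry that answer, least of all for rare serious events.

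**Working it through.** **Inputs from the document.** 40 per arm (5.2.1). Any complication 15.8%, of which 23.9% were Clavien III-IV, in a series of 450 procedures (5.3). The site's matched cohort had 29 per group, with no complications off-clamp and one Clavien-2 complication on-clamp (1.1).

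**Inputs not in the document.** It gives no equivalence margin and no rate for positive margins or recurrence. There is also no stated power or precision figure to reproduce.

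**Planning rates.** Any complication: 15.8%. Clavien III-IV: 0.158 × 0.239 = 0.0378, about 3.8%, taking 23.9% as a share of patients with complications. The site's 1/58 = 1.7% is an any-complication rate; its Clavien III-IV count is 0/58.

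**Simple precision at 15.8% in both arms.** SE = √(2 × 0.158 × 0.842 / 40) = 0.0816. The 95% half-width is 1.96 × 0.0816 = 16.0 points. The 90% half-width, which corresponds to two one-sided 5% tests, is 1.645 × 0.0816 = 13.4 points.

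**Newcombe 95% interval when the arms give identical results.** With Wilson limits l and u around the observed proportion p, the half-width is √((p − l)² + (u − p)²).

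| Result in each arm | Wilson limits | Half-width on difference |
|---|---|---|
| 6/40 (15.0%) | 7.1% to 29.1% | √(7.94² + 14.07²) = 16.2 points |
| 2/40 (5.0%) | 1.4% to 16.5% | √(3.62² + 11.50²) = 12.1 points |
| 0/40 | 0% to 8.8% | 8.8 points |

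The last row is 1.96² / (40 + 1.96²) = 3.84 / 43.84 = 8.8%.

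**Average Newcombe half-width**, enumerating all pairs of binomial counts with equal true rates: 16.2 points at 15.8% and 11.2 points at 3.78%. The simple formula gives only 8.4 points at 3.78%, which is too narrow for counts this sparse.

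**What margin could be met?** For two one-sided 5% tests with no true difference, 80% power needs a margin of (1.645 + 1.282) × 0.0816 = 0.239. That is about 24 points, wider than the 15.8% rate itself. The significance level and power here are my assumptions.

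**How often would the observed rates look similar?** Take 'similar' as counts differing by at most 2 of 40, that is 5 points (an illustrative choice).

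| True rates, off-clamp vs clamped | Chance of looking similar |
|---|---|
| 3.8% vs 3.8% | 87% |
| 7.6% vs 3.8% | 67% |
| 15.8% vs 15.8% | 56% |
| 25.8% vs 15.8% | 30% |

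For serious complications, looking similar barely separates no effect from a doubling.

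**The case against.** The strongest reply is that 'equivalent' is used loosely, in the spirit of section 1.1, where complications are called similar and perioperative outcomes comparable. These are secondary objectives in a trial of about 80 patients, and 9.3 openly declares a descriptive analysis, so no formal equivalence claim is planned. A randomised parallel-group design also implies summaries by arm. Much of this is fair. It lowers the weight of the point but does not remove the mismatch: the stated verb is to determine, and description without a between-arm contrast determines nothing about equivalence. If the loose sense was meant, the rewording costs nothing.

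Three stronger readings are tempting and not supported.

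- A reader might infer that similar observed rates would usually hide real harm. For any complication, a 10-point excess would still look similar only 30% of the time, against 56% under equal rates, so the data carry some information there. The argument is strongest for rare serious events.
- A reader might take the site's 1/58 as a serious-complication rate. Section 1.1 reports a single Clavien-2 event.
- A reader might infer from Appendix C, which counts yearly scans from the three-month visit, that the 2-year disease-free estimate is distorted. Section 7.0 is consistent with that schedule and 5.5 does not contradict it. Any effect is common to both arms, and its size depends on rates the document does not give. It has no bearing on equivalence.

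**Conclusion.** Wrong as written: secondary objectives 1 and 2 claim a determination that the stated analysis cannot make. At 40 per arm, identical results leave 95% intervals on the difference of ±8.8 to ±16.2 points over the cases shown, and about ±11 points on average at a Clavien III-IV rate near 3.8%.

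The mismatch itself rests only on the document's text. The sizes rest on 40 evaluable patients per arm and on the section 5.3 rates applying here. Oncologic precision cannot be tied to planning rates because none are given. Recurrence would be less precise than these figures suggest, since patients with benign pathology leave follow-up at three months (5.5).

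A reader might infer that the trial is too small and must be enlarged. The document plans no equivalence test and states no power for one, so the remedy is to match the claim to the analysis. The primary objective is outside this point.

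**What to change.** **In 2.2**, reword:

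- Objective 1: *To estimate the difference between arms in positive margins and in recurrence, each with a 95% CI.*
- Objective 2: *To estimate the difference between arms in the proportion of patients with any intra- or postoperative complication through 3 months, and with a Clavien grade III or higher complication, each with a 95% CI.*

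**In 9.3**, add:

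- Results are tabulated by arm as randomised, whatever technique was finally used. Section 5.2.2 allows intraoperative conversion, so the analysis set must be named.
- Differences in proportions (off-clamp minus clamped) are given with Newcombe 95% intervals.
- The highest Clavien grade per patient is tabulated by arm.
- Two-year recurrence in patients with malignant pathology is estimated by arm from Kaplan-Meier, with a between-arm difference and a 95% interval that stays valid when an arm has no events, for example by combining Wilson-type single-arm limits. Plain Greenwood limits have zero width in such an arm, and log-log limits are undefined there. With an assumed 32 malignant cases per arm and 95% free of recurrence, the chance that at least one arm has no events is 1 − (1 − 0.95³²)² = 1 − (1 − 0.194)² = 35%.
- No equivalence claim will be made.

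**Cost.** A few sentences in 2.2 and 9.3, and a more modest stated aim. No new patients, visits or data are needed.
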